A2 Primary Hypothesis

The expected results of this project are:

- 1.) identification of stakeholder-informed implementation strategies for mental health interventions tailored for the orthopedic setting,
- 2.) refined digital and printed mental health interventions that are scalable and acceptable to older patients, and
- 3.) requisite planning data to facilitate successful completion of a subsequent clinical trial.

A3 Purpose of the Study Protocol

The goals of this project are to:

- 1.) identify effective implementation strategies to introduce mental health intervention in the context of real-world orthopedic care,
- 2.) optimize the usability of two mental health interventions (Wysa and a novel printed resource guide) for older adult orthopedic patients, and
- 3.) identify the intermediate mechanisms through which Wysa has an effect.

B Background

B1 Prior Literature and Studies

Depression and anxiety heighten musculoskeletal pain and negatively impact outcomes after orthopedic surgery.¹⁻⁵ Targeted mental health treatment can improve both physical and mental health in these patients,⁶⁻⁸ but a gap remains in effectively and routinely engaging orthopedic patients in mental health care in an acceptable, sustainable, and scalable fashion. Barriers include: 1.) limited orthopedic provider time and knowledge to discuss mental health resources,⁹ 2.) patient concerns regarding cost, transportation, and time necessary for mental health treatment,¹⁰⁻¹³ and 3.) a national shortage of mental health professionals.¹⁴ These barriers disproportionately affect minority groups of all types.¹⁵

Our ongoing, funded pilot work suggests that an established digital mental health intervention (Wysa) based on behavioral activation, mindfulness, and sleep health meaningfully improves PROMIS Depression and Anxiety scores in orthopedic patients across the adult age spectrum at one- and two-month follow-up. However, the clinical context (e.g., team member leading the discussion, words used to discuss mental

health, volume of information already discussed during the encounter) influences providers' likelihood of discussing the intervention and patients' interest in trying it.

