Questionnaire-8, and Athens Insomnia Scale) will be collected at baseline and one-month follow-up.²⁰⁻²⁶

C2 Rationale for the Selection of Outcome Measures

Depression and anxiety can worsen musculoskeletal pain and reduce the effectiveness of traditional orthopedic treatments. Nevertheless, addressing mental health is not currently a part of standard treatment for orthopedic conditions. The purpose of this study is to identify strategies to address mental health in the context of orthopedic care in a manner that is feasible, effective, and acceptable to patients and clinicians.

D Study Design

D1 Overview or Design Summary

This study will utilize qualitative cross-sectional and quantitative longitudinal methods. In semi-structured interviews, orthopedic providers and patients with spine conditions will discuss their overall perspectives, specific needs, and preferred solutions to addressing mental health impairment in the context of orthopedic care and research. In these sessions, patient stakeholders will also user test two specific mental health interventions: a customized version of a commercial digital mental health intervention (Wysa) and a prototype of a print-based mental health resource guide. The patient stakeholders will be provided one month of Wysa access, and they will complete baseline and follow-up measures related to usability, clinical effectiveness, and intermediate behavioral mechanisms through which Wysa is hypothesized to act. Wysa usage data will be obtained from the app company. Delivery of Wysa and the printed resource guide will be iteratively refined based on user feedback.^{13,29,34-42}

D2 Subject Selection and Withdrawal

Inclusion Criteria

- WU Orthopedics patients who are presenting to a spine specialist for neck and/or back pain (spine surgeon, physiatrist, or APP within either of those two divisions) for new or return evaluation
- 18+ years old
- Musculoskeletal pain for 3+ months

Exclusion Criteria

- Routine post-op visit, with no plans for further surgery at this time
- Endorses mental health crisis (active suicidal or homicidal ideation, psychosis)
- Cognitive impairment which would interfere with meaningful engagement with research interview, questionnaires, and/or intervention

2.a Subject Recruitment Plans and Consent Process

Providers:

- Eligible providers are already known, through departmental contacts

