- E-mail will be sent to eligible providers in batches until enough interviews have been scheduled and performed to reach data saturation

- *Verbal consent (waiver of written consent) requested for providers, since they will just be participating in semi-structured interviews.

Patients:

- Prospectively and/or retrospectively review clinic schedules for surgical and non-operative orthopedic spine providers
- To reach purposive sampling goals, some potentially eligible patients may be called prior to appointment date to notify them of the study, assess preliminary interest, and ask to plan staying 60-90 minutes after clinic visit in order to participate in study. Also offer to assist with parking expenses (eg parking validation ticket at CAM).
- Patients will officially be screened at the time of and/or after their orthopedic clinic visit to verify eligibility.
- *Written consent for patients when consent is obtained in clinic. Request the option for verbal consent if the participant is consented over the phone/Zoom.

Contact procedures / permission:

Providers:

- Participants will be e-mailed to be invited to participate.
- They will be asked to complete a brief “demographics” descriptive questionnaire.

Patients:

- Participants will be called or approached in person to be invited to participate.
- During the consent process, they will be asked whether they agree for e-mail and/or text messages to be sent to them. Based on their response, a link to the follow-up REDCap survey will be sent via e-mail and/or text message.

Participants will also be called, e-mailed, and/or text messaged as necessary for reminders to complete the survey.

2.b Randomization Method

No randomization method. No control group.

2.c Risks and Benefits

Risks:

You may experience one or more of the risks indicated below from being in this study. In addition to these, there may be other unknown risks, or risks that we did not anticipate, associated with being in this study.

Although very unlikely, subjects participating in this study may feel inconvenienced from completion of multiple surveys and/or uncomfortable answering some of the survey questions. This risk is minimal because participants will be informed of the estimated time commitment and general content of the survey questions before they consent to participate. The seriousness of this risk is low because participants can withdraw from the study at any time.

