One risk of participating in this study is that confidential information about you may be accidentally disclosed. We will use our best efforts to keep the information about you secure. Please see the section in this consent form titled “How will you keep my information confidential?” for more information.

Benefits:

You will not benefit from being in this study.

However, we hope that, in the future, other people might benefit from this study because information obtained from this study may lead to a better understanding of how to treat patients in an orthopaedic clinic who also experience depression and/or anxiety.

2.d Early Withdrawal of Subjects

If a participant would like to withdraw from this study, they can contact the study coordinator who will document when the patient called to withdraw that their data will not be included in any future data analysis from the time of withdrawal.

2.e Treatment Regimen

After agreeing to participate, patient participants will continue their participation in their orthopedic care plan, as directed by their healthcare provider. We will also assist the participant in downloading the Wysa app to their smartphone or other electronic device, if desired. Through the Wysa app, participants can track and manage their emotions, and they can learn research-based techniques to help them feel better and manage any stress or pain they may be dealing with. Participants will have access to research-based wellness tools such as supportive listening, deep breathing techniques, guided meditation, yoga, and more. Participants can communicate with a virtual artificial intelligence (AI) chatbot, and/or they can message a highly trained and qualified human well-being coach. The intended use of the Wysa app is to encourage mental well-being as an early intervention tool in a self-help context. The Wysa app is considered investigational, which means that it has not been approved by the U.S. Food and Drug Administration.

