Participants will have access to the Wysa app services for one month, and they can use any or all of the services as much or as little as they find useful. No one on the Washington University study team will read participants' chats to the Wysa chatbot. Any chats with a human Wysa well-being coach will remain between just the participant and their coach. The study team will only receive information on whether the participant used the Wysa app, how much they used each feature and/or found it helpful. Participants will be e-mailed and/or sent a text message to the follow-up survey link after one month. The surveys will ask them about their current level of wellness and whether they found the app helpful.

•

2.f Method for Assigning Subjects to Treatment Groups

No control group. Everyone in the provider group, gets the same treatment, and everyone in the patient group will get the same treatment.

E Study Procedures***E1 Screening for Eligibility***

Recruitment of orthopedic provider stakeholders:

Three of the study investigators are faculty members within the WU Department of Orthopaedic Surgery. As such, they have professional and personal relationships with the vast majority of the 70+ orthopedic clinicians and their support staff at WU. These relationships will facilitate a high rate of rapid recruitment from this group of stakeholders into the study. In addition to universal secure, virtual meeting capabilities among this group (Zoom-HIPAA), all orthopedic faculty members have dedicated, secure academic office space in which private semi-structured interviews can be conducted in person.

Recruitment of orthopedic patient stakeholders:

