- Suggest that the research places participants or others at a greater risk of harm (including physical, psychological, economic, or social harm) than was previously known or recognized.

5.d Data Collection Procedures for Adverse Events

The research coordinator will document any adverse events reported in a spreadsheet that is password protected and only available to be viewed by the study team.

All adverse events will be reviewed by the principal investigator as they arise.

5.e Reporting Procedures

Events will be reported per the Washington University Institutional Review Board Procedures.

5.f Adverse Event Reporting Period

Events that qualify for immediate reporting described above will be reported within the following timeframe:

- a. 10 working days of the occurrence of the event or notification to the PI or research team of the event.
- b. The death of a research participant should be reported within 1 working day of the occurrence of the event or notification to the PI or research team of the event.

Adverse events/other events that do not require immediate reporting will be provided to the IRB in summary format at the time of continuing review.

F Statistical Plan

F1 Sample Size Determination and Power

No power calculation was performed for this study because the primary aim involves a qualitative analysis. The sample size will be determined by reaching data saturation from the provider and patient stakeholder interviews.

F2 Interim Monitoring and Early Stopping

The Principal Investigator will take responsibility for monitoring patient safety. Patients in the study will be monitored on an as needed basis to assure that they are doing well.

Adverse events will be assessed by [name] to determine if they are serious, unexpected and related to the study procedures.

If a complication should arise, the patient would be previously instructed how to contact the research coordinator.

F3 Statistical Methods

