Interviews will be audio recorded and professionally transcribed. Using inductive and deductive coding approaches based on CFIR and COM-B, a codebook will be developed by one team member, and one or more team members will code all transcripts using NVivo. Group discussion among the research team will be used to resolve coding discrepancies, confirm data saturation has been reached, and organize codes into themes. Scores on the System Usability Scale will be used to iteratively refine both mental health interventions under investigation. Longitudinal PROMIS score changes will be compared between “high” and “low” Wysa users (defined by total Wysa interactions), and associations between changes in behavioral targets (behavioral activation, pain acceptance, sleep quality) and clinical outcomes (depression, anxiety) will be assessed.

G Data Handling and Record Keeping

G1 Confidentiality and Security

Plans to protect the privacy interests of the participants during the conduct of the study:

- 1) Only the minimum necessary private information is collected for the purposes of the study
- 2) Any procedures or interventions conducted as part of the study will be conducted in private setting to the extent possible
- 3) Recruitment/consent will occur in a private setting
- 4) Participants will be able to ask questions in a private setting

Project uses paper and hard copy consents, surveys, data collection forms, research subject binders, or other hard copy materials:

- 1) All materials are stored in secured environment
- 2) Access is limited to research team members only
- 3) Transported securely/shipped with tracking mechanism

Project collects, stores and/or transmits electronic data on mobile devices, desktop computers, servers including cloud servers, email, or any other information in electronic form:

- 1) Password protected
- 2) Access is limited to research team only
- 3) Data in Redcap
- 4) Data in Box
- 5) eCRF system
- 6) Transmitted using recognized security for electronic submission
- 7) Recordings taken during interviews with providers and patients will be reviewed by a study team member, and all personal identifiers will be removed prior to being uploaded into Rev.com to be transcribed into text for qualitative analysis.
- Other

G2 Training

Study coordinator was trained in the Wysa software, and is able to explore the app with the participants in the patient population for use on their own. No formal training is necessary for this study.

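### F3 splits Wysa users into high and low groups at an unstated cut-off; the interaction count, which the team will hold, is better analysed as a continuous variable on a pre-set scale.

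*Combined protocol and SAP*

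**What the plan says.** The document is the combined protocol and SAP. Its only planned analysis linking amount of Wysa use to clinical outcome is one clause in F3: "Longitudinal PROMIS score changes will be compared between “high” and “low” Wysa users (defined by total Wysa interactions"). No section gives the dividing line, says when it will be chosen, names a model or test, or mentions the baseline PROMIS score.

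- **Usage data.** D1 states that "Wysa usage data will be obtained from the app company", and 2.e says the team will receive "information on whether the participant used the Wysa app, how much they used each feature".
- **How use arises.** Under 2.e participants are free in their use: "they can use any or all of the services as much or as little as they find useful". Installation is optional too: "We will also assist the participant in downloading the Wysa app to their smartphone or other electronic device, if desired". Section 2.b adds: "No randomization method. No control group".
- **Sample size.** F1 reports no power calculation and states: "The sample size will be determined by reaching data saturation from the provider and patient stakeholder interviews".
- **Purpose.** A2 lists among the expected results "requisite planning data to facilitate successful completion of a subsequent clinical trial".

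**The concern.** Reducing a count to two groups discards information, and the number of patients is set by interview saturation, so it may be small. Because the cut-off is open, it could also be settled after the PROMIS changes are known, and different reasonable choices can give different estimates from the same data.

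Two smaller gaps follow. F3 does not place participants who never install the app, or say how they differ from those whose usage data are missing or cannot be linked. It also does not say whether the baseline score enters the comparison. That matters because use is self-selected and there is no control group.

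At stake is the reliability of the usage-outcome estimate that the team would carry into planning the later trial. No decision stated in the documents depends on it.

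**Working it through.** The plan gives no sample size, cut-off, usage distribution, correlation or significance level, so there is no figure of its own to reproduce. **Every input below is an assumption:** 20, 30 or 40 patients, PROMIS SD of 10 T-score points, and a correlation r between baseline and follow-up of 0.6 to 0.7 (0.5 to 0.7 in step 4).

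**1. Information lost by splitting.** If outcome is linear in a normally distributed exposure, a split with upper fraction p keeps φ(z)²/[p(1−p)] of the information, where z is the normal cut point.

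- Median: 0.3989²/0.25 = 0.637, a loss of 36%.
- Upper third: 0.3636²/0.2222 = 0.595, a loss of about 41%.
- Upper quartile: 0.3178²/0.1875 = 0.539, a loss of 46%.

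For counts on the log(1 + count) scale, the share kept is the squared correlation between the split and the continuous variable. With a negative binomial count (mean 40, shape 0.7, about 6% zeros), the loss is 35% at the median and 55% at the upper quartile. Adding non-users until 34-44% of participants are at zero reduces the median-split loss to about 16-20%.

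**2. Dependence on the cut-off.** In 20,000 simulated studies per setting with normal use, the high-low difference was computed at the lower quartile, the median and the upper quartile. The table shows how often the three signs were not all the same.

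| True correlation | n = 20 | n = 30 | n = 40 |
|---|---|---|---|
| 0 | 50% | 48% | 50% |
| 0.3 | 29% | 21% | 16% |
| 0.5 | 9% | 3% | 1% |

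The SD of change is 10·√(2(1−r)), which is 8.9 points at r = 0.6 and 7.7 at r = 0.7. With no true association, the three differences typically span 3.0 to 5.0 T-score points (median range: 4.95 at n = 20 and r = 0.6, 3.01 at n = 40 and r = 0.7).

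**3. Precision, expressed as power.** F3 names no test, so a two-sided 5% test serves only as a yardstick. It assumes outcome linear on the scale analysed and use unrelated to baseline.

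| True correlation | Exposure | n = 20 | n = 30 | n = 40 |
|---|---|---|---|---|
| 0.5 | continuous | 65% | 83% | 92% |
| 0.5 | median split | 42% | 61% | 75% |
| 0.3 | continuous | 26% | 37% | 48% |
| 0.3 | median split | 17% | 25% | 32% |

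Shape matters. With skewed counts, n = 30 and correlation 0.5, log(1 + count) gives 83% against 62% for a median split if the truth is log-linear. If the truth is a step exactly at the median, it gives 64% against 70%.

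**4. Baseline score.** Let g be the correlation of use with baseline.

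- If use has no effect given the observed baseline, the change-score slope is 10·g·(r−1) points per SD of use and the adjusted slope is 0. For g = 0.4, r = 0.5 the change-score slope is −2.0; for g = 0.2, r = 0.7 it is −0.6.
- If change is truly unrelated to use, the change-score slope is 0 and the adjusted slope is 10·g·(1−r)/(1−g²). For the same pairs this is 10·0.4·0.5/0.84 = +2.4 and 10·0.2·0.3/0.96 = +0.6.

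Neither slope is right under both mechanisms, and the documents do not say which applies. A continuous exposure does not remove this problem.

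**The case against.** The strongest defence is that this is a pilot with a qualitative primary aim. F3 names no test or significance level, and a high/low contrast is an easily read summary. That stands, and it limits the importance of the point.

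Four stronger readings are tempting but unsupported.

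- **That the cut-off would reverse the result in half of studies.** This holds only with no true association, where the sign is chance. At a correlation of 0.5 it is 1-9%.
- **That a median split always wastes a third or more of the information.** The documents allow for participants who never install the app; if there are many, the loss is much smaller.
- **That the plan has an inflated false-positive rate.** Searching all cuts from the 20th to the 80th percentile would give about 25-28% at a nominal 5%, but F3 commits neither to a test nor to a search.
- **That log(1 + count) is the required form.** No usage distribution is given. It is a reasonable default, and a true step at the chosen cut would favour a split.

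It is also fair to say that two slopes can conflict. With no Wysa effect and use tied to observed baseline, they differ in sign in 13-15% of simulated studies at zero baseline-use correlation and in 31-42% at 0.5. A rule barring interpretation whenever they disagree could therefore leave no usable result, so the adjusted slope should be a sensitivity result only. Finally, F3 does not define what counts as an interaction, and a continuous analysis needs that settled too.

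**Conclusion.** The point holds as a low-cost improvement of minor to moderate importance. The plan splits a count that the team will have in full, at a threshold stated nowhere. For roughly normal use the split costs about 36% of the information at the median and 46% at the upper quartile, less at the median with many non-users. It also leaves the estimate open to the analyst's choice, most seriously when the true association is weak or absent.

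The sizes rest on assumed sample sizes, distributions and correlations; only the direction of the argument comes from the documents. A modest association (correlation 0.3) would be imprecisely estimated either way. No version of this analysis separates an effect of Wysa from the reasons people choose to use it.

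**What to change.** Replace the usage clause in F3 with text to this effect:

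> The main usage analysis will relate the change in each PROMIS score from baseline to one month to total Wysa interactions as a continuous variable. The counting unit and scale will be fixed before outcome data are examined (for example log(1 + count), with a rank correlation as a check). Each slope will be reported with a 95% CI and a scatterplot. The slope adjusted for the baseline value of the same measure will be shown beside it as a sensitivity result. Participants confirmed as non-users count as zero; missing or unlinked usage data are treated as missing, and the number of each is reported. Any high/low display is descriptive, split at the median. All results are exploratory associations, because use is self-selected.

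This needs no new data and no added patient contact. It costs one extra model per PROMIS measure and requires an assumed shape, which the scatterplot and rank correlation help to check. Confounding by self-selected use remains. If the team prefers to keep the split as the main analysis, the cut-off should at least be fixed before outcomes are seen.

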Depression and anxiety worsen musculoskeletal pain and reduce the effectiveness of traditional orthopedic treatments. Nevertheless, addressing mental health is not currently a part of standard treatment for orthopedic conditions. The purpose of this study is to identify strategies to address mental health in the context of orthopedic care in a manner that is feasible, effective, and acceptable to patients and clinicians.

C Study Objectives

C1 Primary Aim

Aim 1: Identify the contextual determinants of implementation success for addressing patients' mental health in the context of orthopedic care.

Using standard qualitative methods, two stakeholder groups will be interviewed: WU orthopedic providers and orthopedic spine patients ≥ 18 years old, with a focus on patients 65 years and older. Using purposive sampling, a goal of at least half of patient stakeholders will be women, and one quarter will identify as an under-represented minority. In semi-structured interviews guided by the Consolidated Framework for Implementation Research (CFIR) and the COM-B model of behavior change, providers and patients will describe needs and preferences related to addressing mental health in a clinical and research context (e.g., recruiting and retaining orthopedic patients in a mental health related randomized controlled trial).

Aim 2: Conduct usability testing for two mental health interventions which can feasibly be implemented in a real-world orthopedic setting: a digital mental health intervention (Wysa) and a novel printed resource guide.

Using semi-structured interviews and the System Usability Scale (SUS), orthopedic patients will participate in an iterative user design process to refine the delivery of Wysa and a printed guide of local and online mental health resources. The printed guide is being prepared as an “enhanced usual care” control intervention for a subsequent R01 randomized controlled trial proposal.^{17,18}

Aim 3: Identify the intermediate mechanisms through which a digital mental health intervention (Wysa) improves mental health symptoms in orthopedic patients.

In a pilot prospective cohort study, patients will receive one month of access to Wysa. Measures of clinical effectiveness (self-reported PROMIS Depression, Anxiety, Pain Interference, and Physical Function¹⁹) and hypothesized behavioral targets (Behavioral Activation for Depression Scale-SF, Chronic Pain Acceptance

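### F3 compares unadjusted PROMIS change between self-selected high and low Wysa users over the same month as the outcome, so a difference can appear, or a real one be hidden, for reasons other than Wysa

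*Combined protocol and SAP*

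**What the plan says.** F3 (Statistical Methods) plans two quantitative outcome analyses. In the first, "Longitudinal PROMIS score changes will be compared between" high and low users, the groups being "defined by total Wysa interactions". In the second, "associations between changes in behavioral targets (behavioral activation, pain acceptance, sleep quality) and clinical outcomes (depression, anxiety) will be assessed". For the first, F3 gives no covariate, no time window for use, no cut-point and no limit on interpretation.

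The rest of the design bears on how that contrast can be read:

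- D2, 2.e (Treatment Regimen): access to the app lasts one month, and the amount of use is left to each patient: "they can use any or all of the services as much or as little as they find useful". Orthopedic care continues alongside.
- C1, Aim 3: the PROMIS and behavioral measures "will be collected at baseline and one-month follow-up". The events chart in E3 shows no assessment in between and marks baseline PROMIS as standard care.
- D2, 2.b: "No randomization method. No control group".
- D2 admits adults from 18 upward, and C1, Aim 1 recruits patients "with a focus on patients 65 years and older".
- C1, Aim 3 is worded on the premise that Wysa improves symptoms. A2 lists planning data for a later trial among the expected results.

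**The concern.** The exposure is chosen by the patient, and by the plan's own terms it depends on perceived usefulness. Someone who starts to feel better may credit the app and keep using it, or may stop because it is no longer needed. Someone who worsens may use it more, or give up. Total use over the month is thus partly a consequence of the outcome. With only two assessments, the data cannot show which came first.

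Confounding adds to this. Patients are recruited across a range of depression and anxiety severity (E1). Baseline severity may influence how much a patient uses the app, and it influences change through regression to the mean. Age varies widely and could also affect both use and symptom course. An unadjusted comparison of change leaves both paths open. Replacing the high/low split with a continuous measure of total use would not close them.

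Aim 3 already takes improvement through Wysa as given, so readers will tend to read a high/low difference as a treatment effect. The study is also meant to inform a randomized trial, so the difference could be taken up as an effect size. The bias can go either way, so the figure could mislead as an optimistic or a pessimistic guide.

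**Working it through.** The documents state no sample size, SD, expected difference or significance level for this contrast, so there is no planned figure to reproduce. The check asks how large a difference can arise when the true Wysa effect is zero.

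**Assumptions (none is in the documents).** Use and PROMIS change are bivariate normal; groups are split at the median of use; SD of change is 5 to 7 T-score points; correlations are as shown; N is 20 to 60; tests are two-sided at 0.05.

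**Route 1: use correlates directly with change (rho).**

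Expected difference between halves = 2 × sqrt(2/π) × rho × SD = 1.596 × rho × SD.

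- rho 0.2, SD 5: 1.596 × 0.2 × 5 = 1.60 points
- rho 0.3, SD 6: 1.596 × 0.3 × 6 = 2.87 points
- rho 0.4, SD 7: 1.596 × 0.4 × 7 = 4.47 points

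A simulation with 20,000 replicates per setting agrees. At rho 0.3 the mean difference is 0.46 to 0.47 SD, against 0.479 SD from the formula. The share of replicates with p < 0.05 under no Wysa effect is:

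- rho 0: 5% at every N
- rho 0.2: 10% (N 20), 17% (N 40), 23% (N 60)
- rho 0.3: 17%, 32%, 45%
- rho 0.4: 28%, 53%, 71%

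These results take use to rise with improvement. If use falls with improvement, the sign reverses and a real benefit could be masked.

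**Route 2: age alone.** If age correlates a with use and b with change, the induced correlation is a × b, and the difference is 1.596 × a × b × SD.

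- a = b = 0.3: 1.596 × 0.09 = 0.144 SD, or 0.86 points at SD 6; simulated false-positive rate 6% to 9% for N 20 to 60
- a = b = 0.5: 1.596 × 0.25 = 0.399 SD, or 2.4 points at SD 6; 13% to 34%

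For age alone to induce rho of 0.2 to 0.4, with a and b equal, each would have to be sqrt(0.2) = 0.45 to sqrt(0.4) = 0.63. Adjusting for age in this scenario brings the mean difference to about zero and the rejection rate to about 5% at every N tried.

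**What adjustment can do.** The age simulation shows that a measured baseline confounder can be handled at low cost. The same reasoning applies to the baseline PROMIS score, although no size was computed for that path. Neither adjustment removes the part of Route 1 in which use responds to improvement during the month.

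**The case against.** The strongest defense is that this is a pilot cohort with a qualitative primary aim, a sample size set by data saturation (F1) and an openly stated lack of control. Self-selection is inherent in any single-arm analysis by use. F3 speaks only of comparing and of associations; it never calls the difference a Wysa effect or says it will be carried forward. That is fair and limits the severity. It does not dispose of the point, because Aim 3 is causally worded, A2 wants planning data, and the remedy is nearly free.

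Three stronger readings are tempting, and the documents do not support them:

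- A reader might infer that age could produce the 1.6 to 4.5 points. That range belongs to a direct use–change correlation. The documents give neither age correlation. A3's aim of improving usability for older patients suggests at most that age matters for use. B1 reports pilot improvement across adult ages, which is no sign that age drives symptom course.
- A reader might infer that this contrast is the only link between Wysa and symptoms. It is the only between-group contrast. PROMIS is also measured before and after access, the follow-up survey asks whether the app helped, and F3 plans change-on-change associations. Those are uncontrolled too, so they do not rescue the causal reading.
- A reader might conclude that first-week use should replace total use. Early use is still self-selected, still falls within the outcome interval and discards most of the exposure. The plan says the company supplies how much each feature was used; it does not show that dated counts are available.

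**Conclusion.** The concern holds for the contrast as planned. Unadjusted change compared by self-chosen use over the same month can differ from zero without any Wysa effect, or conceal a real one. Under a direct use–change correlation of 0.2 to 0.4 and a change SD of 5 to 7, the size is about 1.6 to 4.5 points. Through age at correlations of 0.3 each, it is about 0.9 points at SD 6. Confounding by baseline severity is a clear path but is not quantified here. All these figures rest on assumed correlations, SDs and a median split. They show what can happen, not what will. The documents also do not commit the study to reporting this difference as a treatment effect, so the point is about preventing that reading. It should be corrected, but it does not affect the qualitative primary aim.

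**What to change.** In F3:

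1. Compare one-month PROMIS scores by Wysa use in a regression that includes the baseline value of the same PROMIS score and age. Both are already held: baseline PROMIS comes from standard care, and age is known from eligibility. Analyzing change with the baseline score as a covariate gives the same coefficient for use.
2. State that the result is an exploratory association with use, that it will not be reported as an effect of Wysa, and that it will not be used as the effect size for the next trial.

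Optional: if the app company can supply dated counts, report first-week use as a sensitivity analysis beside total use, not in place of it.

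The cost is some SAP wording and two degrees of freedom, which is noticeable in a small sample. Step 1 reduces confounding by the measured baseline variables but does not remove reverse causation, so step 2 is needed whatever the adjusted analysis shows.
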